- h Electronic diary/NPIF meter is used for daily recording of MFNS use, morning NPIF (daily up to Week 24 and monthly from Week 24 onward) and daily symptoms severity from V1 to end of study): 1) nasal congestion/obstruction 2) anterior rhinorrhea (runny nose), 3) posterior rhinorrhea (post nasal drip), and 4) loss of sense of smell, scored using a 0-3 categorical scale where 0 = no symptoms, 1 = mild symptoms, 2 = moderate symptoms and 3 = severe symptoms); This device is dispensed at V1 and information is downloaded from this device on the other indicated days. For nasal congestion, a severity ≥2 on V1 and a weekly average severity greater than 1 at time of randomization (V2) is required and will be made available to the site to determine patient eligibility. If there are 4 or more measurements collected within 7 days prior to randomization, the baseline will be the average of these measurements; if less than 4 measurements are collected, the baseline will be the average of the most recent 4 prior to randomization.

- i* At baseline (V1 and V2) eligibility to surgery based on Investigator opinion will be assessed. During the study treatment and follow up if rescue medication with SCS is required, oral prednisone or prednisolone will be dispensed by the site to the patient through a scheduled or unscheduled in-clinic visit. Use of oral steroids for rescue treatment of worsening nasal polyps or for another reason will be captured by the Investigator (or designee) on the appropriate page(s) of the e-CRF page and the date and dosing information (daily dose, duration, INN) will be informed. Details on actual or planned date for surgery for NP, type and outcome (whenever possible) of surgery will be recorded in a specific e-CRF page. If surgery is performed during the study treatment period or follow-up an AE or SAE page will be completed. Patients will be discontinued from study treatment and assessed as soon as possible using the procedures normally planned for the EOT Visit and will be instructed to return to the study site as described in [Section 10.3.1](#). If surgery is scheduled after the planned end of study, EOS visit will not be delayed. A follow up contact(s) should be performed around the time of planned surgery to document the surgery date and outcome. Surgery data will be collected until e-CRF closure of the trial.

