## **8.2.2 Rescue treatment**

During the study treatment period and off treatment follow-up, based on clinical evaluation, in case of worsening of signs and/or symptoms requiring medical intervention, the Investigator may consider rescue treatment with:

- Nasal lavage with saline and/or systemic antibiotics (up to 2 weeks in case of acute infection).
- Short course OCS (prednisone or prednisolone up to 2 weeks).
- Sino-nasal surgery for nasal polyps. Based on previous observations from PoC study, 8 weeks of IMP treatment is recommended prior to surgery to allow onset of treatment effect.

Patients receiving rescue treatment other than surgery during the study should continue on study drug unless the Investigator decides to withdraw the study treatment. Before starting treatment with SCS patients should come to the study site for the clinical assessments including endoscopy and PROs.

For patients who undergo or are planned for surgery for NP the Investigator may decide to continue IMP up to the time of surgery or end of treatment whichever date comes first (see [Section 9.2.1.5](#) for details). At the time of surgery patients will be permanently discontinued from study treatment and assessed as soon as possible using the procedures normally planned for the end-of-treatment (EOT) Visit as described in [Section 10.3.1](#).

In any case patients who prematurely discontinued the treatment will be encouraged to return to the study site for the efficacy and safety assessments planned at EOT visit and for additional visits as described in [Section 10.3.1](#).

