The observed mean LMK reduction of the dupilumab group with qw dosing in ACT12340 is 9.07 and the observed mean LMK reduction of the placebo group is 0.23. Using same conservative approach that assumes the placebo-adjusted LMK reduction of the dupilumab 300 mg q2w group is 80% of the dupilumab 300 mg qw, the mean LMK reduction of the dupilumab 300 mg q2w group is then assumed to be  $7.30 = 0.8 * (9.07 - 0.23) + 0.23$ . Assuming normal distribution of the change in LMK, a common standard deviation (SD) of 5.50, which has incorporated a 20% inflation from the observed SD in ACT12340, and a 25% dropout rate, with 240 patients for the q2w pool and 120 patients in placebo, the study will have 99% power to detect an effect size of 1.285 using a two-sided test with  $\alpha = 0.05$  for the change in LMK at Week 24 in the dupilumab 300 mg q2w group.

Therefore, with a sample size of 240 patients for the q2w pool ( Arm A and B) at Week 24, the combined power of the three co-primary efficacy endpoints for Japan is at least 97% for dupilumab 300mg q2w group with  $\alpha = 0.05$  assuming no negative correlation between the 3 endpoints.

The sample size is also chosen to enable an adequate characterization of the efficacy between dupilumab 300 mg q2w (pooled A and B arms) and placebo with regard to the key secondary endpoints at Week 24, the change from baseline in the TSS, UPSIT score, the daily loss of smell assessment, the LMK, and the SNOT-22 scores, as well as the proportion of patients receiving SCS and/or planned to undergo surgery for nasal polyps.

Assuming the proportion of patients receiving SCS for NP and/or planned to undergo surgery for NP is 15% in the placebo group, and is 5% in the dupilumab group, with 240 patients for the q2w pool and 120 patients in placebo, the study will have 87% power to detect a hazard ratio of 0.316 between the treatment groups using a two-sided log rank test with  $\alpha = 0.05$ .

With 240 patients for the q2w pool and 120 patients in placebo, the study will have greater than 99% power to detect difference between the treatment groups for all other five key secondary endpoints at Week 24, using a similar assumption procedure as the change from baseline in NC and NPS at Week 24.

The sample size calculations were performed using nQuery Advisor 7.

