information (daily dose, duration, INN) on the appropriate page(s) of the e-CRF. Indication for SCS use is captured by selecting one or more of the following categories:

1. Nasal polyposis.
2. Asthma.
3. Other respiratory disease (specify).
4. Other ear, nose or throat disease (specify).
5. Other reason (specify).

Surgery (actual or planned) for NP

For patients who undergo or are planned for sino-nasal surgery for NP, the reason (worsening signs and/or symptoms during the study), the date of decision for surgery, the planned date and the effective surgery date, the type and outcome of surgery is recorded in a specific e-CRF page. If surgery:

- Is performed during the study treatment period, patient and investigator may decide to continue IMP up to the time of surgery or EOT whichever date comes first. At the time of surgery patients will be permanently discontinued from study treatment and assessed as soon as possible using the procedures normally planned for the EOT Visit and will be instructed to return to the study site as described in protocol. An AE or serious adverse event (SAE) page will be completed.
- Is performed during the follow-up, the patients will be assessed according to the procedures normally planned for the EOS Visit and will be instructed to return to the study site as described in protocol. An AE or SAE page will be completed.
- If surgery date is scheduled after the planned end of study, EOS visit will not be delayed. A follow up contact(s) should be performed around the time of planned surgery to document the surgery date and outcome. Surgery data will be collected until e-CRF closure of the trial.

2.1.3.2.1.7 Spirometry

Spirometry is performed at local level (study site or another facility) in the morning after withholding the last dose of salbutamol/albuterol or levosalbutamol/levalbuterol for at least 6 hours. Forced expiratory volume in one second (FEV1), forced vital capacity (FVC) and forced expiratory flow at 25% to 75% of forced vital capacity (FEF 25-75) were determined at the designated treatment visits.(9). The results of FEV1 (score in L, % of predicted normal,), FVC and FEF 25-75 were recorded in the e-CRF anytime during run-in period (before V2) for all patients and in patients with asthma for the other scheduled visits during the randomized treatment period.

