2.4.5 Analyses of safety data

The summary of safety results will be presented by treatment group.

General common rules

All safety analyses will be performed on the safety population as defined in [Section 2.3.2](#), unless otherwise specified, using the following common rules:

- The baseline value is defined as the last available value before the first dose of IMP.
- The potentially clinically significant abnormality (PCSA) values are defined as abnormal values considered medically important by the Sponsor according to predefined criteria/thresholds based on literature review and defined by the Sponsor for clinical laboratory tests, vital signs, and ECG [[Appendix A](#)]
- PCSA criteria will determine which patients had at least 1 PCSA during the treatment-emergent adverse event period, taking into account all evaluations performed during the treatment-emergent adverse event period, including nonscheduled or repeated evaluations. The number of all such patients will be the numerator for the on-treatment PCSA percentage
- The treatment-emergent PCSA denominator by group for a given parameter will be based on the number of patients assessed for that given parameter in the treatment-emergent adverse event period by treatment group on the safety population.
- For quantitative safety parameters based on central laboratory/reading measurements, descriptive statistics will be used to summarize results and change from baseline values by visit and treatment group. Summaries will include the endpoint value and/or the worst on-treatment value. The endpoint value is commonly defined as the value collected at the end of treatment. If this value is missing, this endpoint value will be the closest value prior to the end of treatment epoch. The worst value is defined as the nadir and /or the peak post-baseline (up to the end of treatment epoch or EOT) according to the direction (minimum or maximum) of the abnormality as defined in the PCSA list
- The analysis of the safety variables will be essentially descriptive and no systematic testing is planned. Relative risks versus placebo and their 95% confidence intervals may be provided, if relevant
- All safety values including unscheduled measurements will be assigned to the appropriate safety analysis visit window defined in [Section 2.5.3](#).

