2.4.5.1 Analyses of adverse events

Generalities

The primary focus of adverse event reporting will be on treatment-emergent adverse events. Pretreatment and posttreatment adverse events will be described separately.

If an adverse event date/time of onset (occurrence, worsening, or becoming serious) is incomplete, an imputation algorithm will be used to classify the adverse event as pretreatment, treatment-emergent, or posttreatment. The algorithm for imputing date/time of onset will be conservative and will classify an adverse event as treatment emergent unless there is definitive information to determine it is pretreatment or posttreatment. Details on classification of adverse events with missing or partial onset dates are provided in [Section 2.5.2](#).

Adverse event incidence tables will present by SOC, HLG, HLT, and PT, sorted in alphabetical order for each treatment group, the number (n) and percentage (%) of patients experiencing an adverse event. Multiple occurrences of the same event in the same patient will be counted only once in the tables within a treatment phase. The denominator for computation of percentages is the safety population within each treatment group.

Sorting within tables ensures the same presentation for the set of all adverse events within the observation period (pretreatment, treatment-emergent, and posttreatment). For that purpose, the table of all treatment-emergent adverse events presented by SOC and PT sorted by the internationally agreed SOC order and decreasing frequency of PTs within SOCs will define the presentation order for all other tables unless otherwise specified. Sorting will be based on results for the dupilumab 300 mg q2w group.

Analysis of all treatment-emergent adverse events

The following treatment-emergent adverse event summaries will be generated for the safety population.

- Overview of treatment-emergent adverse events, summarizing number (%) of patients with any
 - Treatment-emergent adverse event
 - Serious treatment-emergent adverse event
 - Treatment-emergent adverse event leading to death
 - Treatment-emergent adverse event leading to permanent treatment discontinuation
- All treatment-emergent adverse event by primary SOC, HLG, HLT, and PT, showing number (%) of patients with at least 1 treatment-emergent adverse event sorted by the SOC internationally agreed order. The other levels (HLG, HLT, PT) will be presented in alphabetical order

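### NP surgery performed on study counts in the rescue endpoint and again in the AE or SAE totals, and the SAP plans no safety summary that separates the two

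*SAP*

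**What the plan says.** **Efficacy side.** SAP 2.4.4.2.3 defines the rescue event as the first use of systemic corticosteroids (SCS) or NP surgery, actual or planned.

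**Safety side.** Footnote i of the flow chart in Protocol 1.2 states: "If surgery is performed during the study treatment period or follow-up an AE or SAE page will be completed". SAP 2.1.3.2.1.6 repeats the rule for both periods: "An AE or serious adverse event (SAE) page will be completed". For surgery scheduled after the planned end of study, only the date and outcome are collected.

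**Study drug.** Protocol 8.2.2 states: "At the time of surgery patients will be permanently discontinued from study treatment".

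**Safety analysis.** SAP 2.1.4 runs the treatment-emergent period to 98 days after the last dose. The overview in SAP 2.4.5.1 has lines for any TEAE, serious TEAEs, and "Treatment-emergent adverse event leading to permanent treatment discontinuation". Neither that section nor the AE groupings in Table 1 of SAP 2.1.4.1 flags, excludes or separately summarises NP surgery. SAP 2.4.5 calls the safety analysis essentially descriptive and adds: "Relative risks versus placebo and their 95% confidence intervals may be provided".

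**The concern.** An operation for polyps on study is first of all a treatment failure, and the trial is designed to show fewer of these on dupilumab. If the same operation is also a TEAE, sometimes a serious one, and perhaps the recorded reason for stopping study drug, the one-line safety totals carry part of the efficacy result. A lower SAE or discontinuation percentage on dupilumab could then reflect fewer polyp operations rather than better tolerability. A modest excess of other events on dupilumab could also be diluted in those totals. They are the figures a reader compares first, and the figures from which relative risks would be computed.

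**Working it through.** **1. Which operations are counted, and where**

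| Operation | Rescue endpoint | AE or SAE page | Ends study drug |
|---|---|---|---|
| Performed during treatment | yes | yes | yes |
| Performed during follow-up | if decided during the treatment period | yes | already ended |
| Planned during treatment, not performed by end of study | yes | none stated | not for this reason |

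The last dose is at Week 50 (Protocol 8.1.4). Adding 98 days (14 weeks) gives Week 64, so for a completer the treatment-emergent window also covers follow-up. Only operations meeting a seriousness criterion, such as inpatient hospitalisation (Protocol 10.4.1.2), enter the SAE tables. Entry as a TEAE leading to discontinuation is likely, because Protocol 10.4.3 has the action taken with study drug recorded for each AE. Neither document says how that field is completed for surgery.

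**2. The plan's own figure**

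The inputs are in Protocol 11.1. For placebo it reads: "Assuming the proportion of patients receiving SCS for NP and/or planned to undergo surgery for NP is 15% in the placebo group". The planned dupilumab rate is 5%, and the comparison sets 240 patients from Arms A and B against 120 from Arm C. The stated result is that "the study will have 87% power to detect a hazard ratio of 0.316 between the treatment groups".

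- Hazard ratio: ln(0.95)/ln(0.85) = 0.316, as stated.
- Expected events: 120 × 0.15 = 18 on placebo and 240 × 0.05 = 12 on dupilumab.
- Two-proportion test, pooled variance under the null: pooled rate 30/360 = 0.0833; null SE = √(0.0833 × 0.9167 × (1/120 + 1/240)) = 0.0309; alternative SE = √(0.15 × 0.85/120 + 0.05 × 0.95/240) = 0.0355. Power = Φ((0.10 − 1.96 × 0.0309)/0.0355) = 86.7%.
- Wald test on the log hazard ratio: Φ(1.152/√(1/18 + 1/12) − 1.96) = 87.1%.

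The stated 87% reproduces. The planning assumption is therefore a threefold difference in rescue, but for a composite that includes SCS.

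**3. How far operations could move the SAE total**

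The documents do not give the share of rescue events that are performed operations (s), the share of those that are serious (q), or the percentage of patients with another SAE (b). I assume s = 10-50%, q = 50-100% and b = 5% in each arm, with other SAEs independent of surgery. I also apply the 5% planned for the q2w pool to any dupilumab arm.

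Displayed percentage = 1 − (1 − b)(1 − r·s·q), with r = 0.15 on placebo and 0.05 on dupilumab. The true relative risk is 1.0 throughout.

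| s | Operated, placebo / dupilumab | q | SAE displayed, placebo / dupilumab | Displayed RR |
|---|---|---|---|---|
| 10% | 1.5% / 0.5% | 50% | 5.7% / 5.2% | 0.92 |
| 10% | 1.5% / 0.5% | 100% | 6.4% / 5.5% | 0.85 |
| 25% | 3.75% / 1.25% | 50% | 6.8% / 5.6% | 0.82 |
| 25% | 3.75% / 1.25% | 100% | 8.6% / 6.2% | 0.72 |
| 50% | 7.5% / 2.5% | 50% | 8.6% / 6.2% | 0.72 |
| 50% | 7.5% / 2.5% | 100% | 12.1% / 7.4% | 0.61 |

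With b = 3% the range is 0.87 to 0.53. With b = 10% it is 0.96 to 0.73.

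**4. Other totals**

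For any TEAE and for TEAEs leading to discontinuation, operations can add a gap of at most 1.0 to 5.0 points at s = 10-50%. The gap is smaller to the extent that operated patients already have another such event. For discontinuation, the operation must also fall in the treatment period and be recorded as the reason for stopping. The ceiling is 10 points, if every rescue event were a performed operation.

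**5. An opposing effect**

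Surgery during treatment stops study drug, and the treatment-emergent window then closes 98 days after the last dose. Operated patients, expected to be more frequent on placebo, have less time to accrue other events. This lowers the crude placebo percentage and is not in the table. SAP 2.4.5.1 adjusts for exposure only for AESIs and selected groupings.

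**The case against.** The strongest case against is that little is hidden. SAP 2.4.5.1 tabulates serious TEAEs by system organ class and preferred term and by relationship, with a full listing, and tabulates discontinuations by preferred term. SAP 2.2 reports stopping by main reason and rescue by type. SAP 2.4.4.5.2 analyses surgery alone. At s = 50% there would be about 9 operations among 120 placebo patients and 6 among 240 on dupilumab, few enough to find. No test or decision rule uses the totals. Short-course oral steroids are also a rescue option, and 8 weeks of treatment is recommended before surgery (Protocol 8.2.2), so the surgery share may be low.

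Most of this stands and limits the point to the patient totals. It does not remove it. Preferred-term tables count a patient under every term, so the number with any SAE other than NP surgery cannot be read from them. It can be rebuilt by hand from the listing, but without a rule fixed in advance. Protocol 10.4.3 prefers a diagnosis to symptoms, so an operation may be entered as the procedure or as worsening polyposis and scatter across terms.

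A reader might infer that every NP operation becomes an SAE and ends treatment. The text does not support that: planned-only and post-study surgery have no stated AE page, the page is AE or SAE, nothing says the surgery is inpatient, and only surgery in the treatment period stops study drug. A reader might also infer that a real SAE excess on dupilumab would be masked. The listing and term-level tables make that unlikely beyond the totals.

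**Conclusion.** The point holds as a gap in safety presentation. NP surgery performed on study feeds both the rescue endpoint and the safety totals, and SAP 2.4.5.1 has no summary that separates them. The direction probably favours dupilumab. That is an expectation from the planned 15% vs 5% composite, not a demonstrated result.

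The size cannot be fixed. Under the stated assumptions a true SAE relative risk of 1.0 would appear as about 0.92 to 0.61, before the partial offset from shorter placebo observation. The lower end needs half of rescue events to be operations and all of them to be serious. The effect on discontinuation totals is probable rather than certain.

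It would go too far to conclude that the main safety comparison should rest on tables without these events. That would remove serious events, and deciding which polyp worsening led to surgery is a judgement. It could also obscure worsening after Arm B moves to q4w dosing, which Protocol 11.4.2.4.3 sets out to describe.

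**What to change.** In SAP 2.4.5.1, before unblinding:

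- Define an NP-surgery event by linking the AE record to the dedicated surgery eCRF page, whether it is entered as a procedure or a diagnosis. Complications of surgery stay counted.
- State how the action taken with study drug on these records is classified for the discontinuation table.
- Add supplementary versions of the TEAE overview, the SAE summary and the discontinuation summary that exclude these events.
- Give any relative risks versus placebo both ways.
- Keep the all-event tables as primary.

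The cost is one linkage rule and a few extra tables. Site reporting and data collection do not change.

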2.1.3.2.2 Other secondary efficacy endpoints

2.1.3.2.2.1 Visual analogue scale

The visual analogue scale (VAS) for rhinosinusitis is used to evaluate the total severity (1). Rhinosinusitis disease can be divided into MILD, MODERATE and SEVERE based on total severity VAS score (0 to 10 cm):

- MILD = VAS 0 to 3.
- MODERATE = VAS >3 to 7.
- SEVERE = VAS >7 to 10.

The patient is asked to indicate on a VAS the answer to the question below:

“How troublesome are your symptoms of your rhinosinusitis”

The VAS ranks from 0 (Not troublesome) to 10 (Worst thinkable troublesome).

2.1.3.2.2.2 Nasal peak inspiratory flow

Nasal peak inspiratory flow (NPIF) evaluation represents a physiologic measure of the air flow through both nasal cavities during forced inspiration expressed in liters per minute. The NPIF is the best validated technique for the evaluation of nasal flow through the nose. Nasal inspiration correlates most with the subjective feeling of obstruction and is the best validated technique for monitoring nasal flow in clinical trials.

On V1 patients will be issued an NPIF meter for recording morning (AM) NPIF. Patients will be instructed on the use of the device, and written instructions on the use of the NPIF meter will be provided to the patients. In addition, the Investigator will instruct the patients on how to record the following variables in the e-diary on a daily basis.

- AM NPIF performed within 15 minutes after arising (before 12 noon) prior to taking MFNS.

Three NPIF efforts will be performed by the patient; all 3 values will be recorded by the patient in the e-diary, and the highest value will be used for evaluation. The procedure takes about 5 minutes.

Baseline AM NPIF will be the mean AM measurement recorded for the 7 days prior to the first dose of IMP. If less than 4 measurements are collected during the 7 days prior to randomization, the average of the most recent 4 prior to randomization during the run-in period will serve as the baseline as described in Section 2.1.1.

The NPIF will be performed daily from V1 to V8 (Week 24). After V8 the NPIF will be performed every 4 weeks.

The nasal flow is expressed in liter per minute, and consecutive measurements are performed.

2.1.3.2.2.3 Asthma Control Questionnaire, 6-question version (ACQ-6) in those patients comorbid with asthma

The asthma control questionnaire-6 (ACQ-6) was designed to measure both the adequacy of asthma control and change in asthma control which occurs either spontaneously or as a result of treatment. Only patients with co-morbid asthma will be asked to complete the questionnaire in the e-diary during clinic visits. Patients should complete the questionnaire before the spirometry test.

The asthma control questionnaire-6 (ACQ-6) has 6 questions which assess the most common asthma symptoms:

- Frequency in past week awoken by asthma during the night.
- Severity of asthma symptoms in the morning.
- Limitation of daily activities due to asthma.
- Shortness of breath due to asthma.
- Frequency of wheezing, and
- Short-acting bronchodilator use.

Patients are asked to recall how their asthma has been during the previous week and to respond to the symptom questions on a 7-point scale (0 = no impairment, 6 = maximum impairment) (see [Appendix C](#)).

A global score is calculated: the questions are equally weighted and the ACQ-6 score is the mean of the 6 questions and, therefore, between 0 (totally controlled) and 6 (severely uncontrolled). Higher score indicates lower asthma control. Patients with a score below 1.0 reflect adequately controlled asthma and patients with scores above 1.0 reflect inadequately controlled asthma. On the 7-point scale of the ACQ-6, a change or difference in score of 0.5 is the smallest change that can be considered clinically important, corresponding to the Minimal Clinically Important Difference (MCID) defined by the developer.

Measurement properties such as reliability and ability to detect change have been documented in the literature ([10](#)).

